## 7. MOLECULAR AND CORRELATIVE STUDIES

### 7.1 Repeat Biopsies for Molecular Testing

It is expected that all patients will undergo a repeat tumor tissue biopsy at the time of removal from study treatment. Ideally, the lesion to be biopsied should be new or growing on BIBW 2992 therapy. The purpose of this biopsy is to assess for the presence or absence of the resistance mutation T790M. This is the primary end-point of the study. In most cases, the repeat biopsy will be at the time of clinical progression. If a patient is being removed from treatment for reasons other than clinical progression (e.g. withdrawal of consent, intolerance of side effects, etc) then a repeat biopsy is desirable but not required.

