### 5.10 Duration of Therapy

Duration of therapy will depend on individual response, evidence of disease progression and tolerance. In the absence of treatment delays due to adverse events, treatment may be given continuously until one of the following criteria applies:

- Disease progression by RECIST criteria (see Section 8.3) Note that if a patient has progression by RECIST but is still deriving clinical benefit and there is not likely to be harm from continuing treatment, patients may continue therapy until no longer clinically benefitting, after discussion with and approval by the Sponsor, [name].
- Retreatment criteria are not met within the specified time frame (see Section 5.5)
- Intercurrent illness that prevents further administration of treatment,
- Unacceptable adverse event(s),
- Participant decides to withdraw from the study, or
- General or specific changes in the participant's condition render the participant unacceptable for further treatment in the opinion of the treating investigator.
- Death
- Lost to follow-up

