## 7.2 Circulating Tumor Cell Studies

Blood samples for CTC analysis will be collected at the following time points.

CONFIDENTIAL

This document is confidential. Do not disclose or use except as authorized.

- Day 1, prior to therapy
- Day 1, three hours after dose
- Day 8
- Day 15
- Cycle 2, day 1
- Cycle 3, day 1
- Cycle 4, day 1
- Cycle 5, day 1
- Then every 2 cycles
- At the time of progression (end of study visit)

CTCs will be assessed from each peripheral blood using the CTC-Chip (see Section 2.3.2). This assay will be performed under the supervision of [name]. Blood samples will be same-day couriered to the [name] Lab in the Charlestown Navy Yard at MGH. Blood samples will be stored on a rocking platform to prevent cell settling and will be processed within 24 hours of blood draw. Whole blood will be passed through the CTC-chip using standard procedures as previously published. Captured CTCs will be fixed on the CTC-chip and stained to identify DNA content, epithelial cells and nonspecifically bound leukocytes. Cells staining positive for nuclear content and positive for cytokeratin will be counted as CTCs. The number of CTCs per milliliter of blood will be determined by comprehensive image analysis, scanning the entire chip and identifying CTCs based on cell size, morphology and fluorescence staining. The association of CTC numbers with radiographic disease response and recurrence will be assessed.

Captured CTCs will then be lysed and DNA content will be collected. Allele-specific sensitive methods will be used to determine the T790M status of the captured cells, as previously published. If sufficient material is available, exploratory analyses will also be performed such as whole genome amplification of DNA and analysis with the SNaPshot platform. CTC-based genotypes will then be correlated with tumor-derived genotypes.

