**CTC collection at MGH only.**
- h Assessment of Requirements for Repeat Biopsy** – To be performed at the time of progression, see Section 7.1.1. Includes interventional radiology review of films for biopsy, holding of anti-platelet and anti-coagulation medications, assessment of PT, PLTs. **Repeat biopsy** should be performed as in Section 7.1 and submitted for molecular analysis and the patient should be seen for a follow-up visit to assess post-biopsy complications at 7 days ( $\pm$  2 days) and at  $\geq$  30 days post-biopsy
- i Survival follow-up** - After discontinuation from the study for any reason, where possible the patient, patient's family, or the patient's current physician must be contacted every 12 weeks for survival information until death. All subsequent chemotherapy, radiation, surgical or other anti-cancer therapies are to be collected until death. A statement of death form should be submitted at any point during the study when a patient has died. In addition, any patient who discontinued study treatment for reasons other than objective disease progression should continue, where possible, to have objective tumor assessments every 8-12 weeks in order to collect information on progression of disease.

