## **12. STATISTICAL CONSIDERATIONS**

### **12.1 Study Design/Endpoints**

This is a pilot study examining the feasibility of using acquisition of a resistance mutation as the primary endpoint for a clinical trial. NSCLC patients with EGFR mutations are highly likely to respond well to EGFR TK inhibition with either first-generation EGFR TKIs (erlotinib, gefitinib) or with the second-generation irreversible inhibitor BIBW 2992, but resistance ultimately develops, see Background. Current literature consistently estimates that fifty percent of resistance to first-generation TKIs is due to the development of a secondary EGFR mutation in exon 20, the point mutation T790M. Since the novel irreversible pan-HER inhibitor BIBW 2992 is highly active in lung cancers harboring activating EGFR mutations and can inhibit the EGFR T790M moiety in pre-clinical studies, a key question is whether BIBW 2992 can suppress the development of clinical resistance via T790M in lung cancer patients.

The study will consist of 24 TKI-naïve patients with mutations in EGFR. Given our relatively large population of referral patients at DF/HCC with EGFR mutations and the collaboration with a few select other centers, This sample size was felt to be feasible to enroll within a three year time period. Each subject will be expected to remain on therapy for approximately 10 months. Therefore within 3.5 years it is expected that we will complete at least 16 of the progression biopsies.

All patients will initially be treated with BIBW 2992 at 40 mg daily, though as in other studies with this compound, dose escalation to 50 mg will be permitted for individual patients after one cycle if there are minimal adverse events at 40 mg. Tumor tissue biopsy for comprehensive genomic profiling is mandatory at the time of acquired resistance (clinical progression). The primary endpoint will be to determine the proportion of patients with T790M resistance mutations at the time of progression. The data collected will be vital in determining the optimal strategy for future studies comparing the efficacy of BIBW 2992 to first-generation EGFR TKIs.

The primary objective is:

1. To determine the proportion of patients that have a T790M mutation on their progression biopsy and to compare this with published data for first-generation EGFR tyrosine kinase inhibitors

The secondary objectives are:

1. To estimate the response rate
2. To estimate the progression-free and overall survival

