## 12.2 Sample Size/Power Calculation for the Primary Endpoint

Based on prior data the rate of T790M at the time of progression on first-generation EGFR TKIs (gefitinib/erlotinib) is 50%.

The null hypothesis is that BIBW 2992 therapy yields the same rate of T790M at the time of progression (50%).

It is expected that approximately 6 of the patients will not undergo a repeat biopsy, despite consenting to the biopsy at the time of enrollment. Reasons for not having a biopsy may include patient withdrawal of consent or not having a lesion that is safe and feasible to biopsy at the time of progression. Therefore, power calculations were performed assuming there would be 18 biopsies performed.

With 18 biopsies and a significance level of 0.05, and using a one-sided binomial test, we can achieve 86% power to detect the alternative hypothesis that BIBW 2992 therapy yields a 20% rate of T790M at the time of progression. The alternate hypothesis implies that BIBW 2992 may be better at suppressing T790M as a mechanism of acquired drug resistance.

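### The endpoint biopsy is tied to removal from treatment in one section and to progression in others, and Section 12.3 admits any repeat biopsy to a test defined at progression

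*Combined protocol and SAP*

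**What the plan says.** **Biopsy timing.** Section 7.1 anchors the biopsy to the end of drug: "It is expected that all patients will undergo a repeat tumor tissue biopsy at the time of removal from study treatment". It adds that in most cases this will be at clinical progression. For a patient removed for another reason, such as intolerance, it calls a biopsy desirable but not required.

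Other sections use progression. Section 1.1 defines the primary endpoint at progression. Section 3.1.4 asks for consent to a biopsy at disease progression. Section 5.1 says clinical progression. Section 12.1 makes the biopsy mandatory at acquired resistance, which it equates with clinical progression. None of these terms is defined against RECIST progression.

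**Study calendar (Section 9).** The biopsy sits in the off-study column. That visit is triggered by meeting the discontinuation criteria of Section 5.10. The biopsy footnote says of the assessment of biopsy requirements "To be performed at the time of progression, see Section 7.1.1", and sends the biopsy itself back to Section 7.1.

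**Treatment past progression.** Section 5.10 lists RECIST progression as a stopping criterion, then adds an exception: "patients may continue therapy until no longer clinically benefitting, after discussion with and approval by the Sponsor". It gives no time limit.

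**CTC sample.** Section 7.2 treats progression and the end-of-study visit as one time point.

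**Analysis.** Section 12.2 sets the null rate at 50% at the time of progression, against "the alternative hypothesis that BIBW 2992 therapy yields a 20% rate of T790M at the time of progression". Its power statement is "With 18 biopsies and a significance level of 0.05, and using a one-sided binomial test, we can achieve 86% power". Section 12.3 makes every patient with a repeat biopsy evaluable and leaves out those without one. It sets no window and does not require progression.

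**The concern.** The biopsy is the only measurement behind the primary endpoint, and both hypotheses describe T790M at progression. Two kinds of sample that do not fit this description can enter the analysis if the plan is followed as written.

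1. **Late biopsies.** A patient kept on drug past RECIST progression and biopsied at removal is sampled at an unspecified later time. By the plan's own account, T790M may be present in a few cells before treatment and grow under selection (Sections 2.3.2 and 2.4). Its status may therefore depend on how long a resistant tumour stays under drug.
2. **Biopsies without progression.** A patient removed for intolerance who agrees to a biopsy has not shown acquired resistance. Section 2.4 says the pre-treatment fraction is not detectable by standard sequencing. A negative result is then plausible for a reason unrelated to suppression of T790M, yet it counts as a success for the drug.

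The second kind pushes towards a false positive conclusion. This sits oddly with Section 12.3, which deliberately takes the conservative side for assay failures by counting them as T790M-positive.

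**Working it through.** **Inputs.** From Section 12.2: n = 18 biopsies, null rate 0.50, alternative rate 0.20, one-sided exact binomial test, alpha 0.05. From Sections 7.1 and 12.3: biopsies without progression are permitted and counted. Assumed, because the documents give no figures: the number k of such biopsies (1 to 3) and their T790M rate q (0 to 0.25).

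**Step 1: the plan's own figure.** Let X be the number of T790M-positive biopsies. Take the largest c with P(X ≤ c | 18, 0.5) ≤ 0.05.

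- P(X ≤ 5 | 18, 0.5) = 12,616 / 262,144 = 0.0481
- P(X ≤ 6 | 18, 0.5) = 31,180 / 262,144 = 0.1189

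So the test rejects at 5 or fewer positives. Power is P(X ≤ 5 | 18, 0.2) = 0.867, which reproduces the stated 86%.

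**Step 2: biopsies without progression.** Keep the rule of 5 or fewer. Under the null, 18 − k biopsies have rate 0.5 and k have rate q. With B the number of positives among the k:

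Type I error = Σ P(B = b | k, q) × P(A ≤ 5 − b | 18 − k, 0.5), summed over b = 0 to k.

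With q = 0, every such biopsy is negative and the sum is P(A ≤ 5 | 18 − k, 0.5). With q = 0.25:

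- k = 1: 0.75 × 0.0717 + 0.25 × 0.0245 = 0.060
- k = 2: 0.5625 × 0.1051 + 0.375 × 0.0384 + 0.0625 × 0.0106 = 0.074
- k = 3: 0.4219 × 0.1509 + 0.4219 × 0.0592 + 0.1406 × 0.0176 + 0.0156 × 0.0037 = 0.091

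| Biopsies without progression (k of 18) | Type I error, q = 0 | Type I error, q = 0.25 |
|---|---|---|
| 0 | 4.8% | 4.8% |
| 1 | 7.2% | 6.0% |
| 2 | 10.5% | 7.4% |
| 3 | 15.1% | 9.1% |

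**Step 3: late biopsies.** Here the sign is unknown. If one late biopsy had an assumed 25% rate, the error is the 6.0% above. If it had an assumed 75% rate, the error is 0.25 × 0.0717 + 0.75 × 0.0245 = 3.6%. The documents do not say which is nearer the truth.

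**Step 4: the dates for one patient.** Take a patient with RECIST progression at a scheduled scan who continues drug under Section 5.10. Section 7.1 places the biopsy at the later removal. Section 12.2 defines the hypotheses at progression. The calendar's off-study visit points to Section 5.10, which contains both the stopping rule and its exception, so it does not settle the matter. Section 12.3 accepts the biopsy whichever date was used.

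**The case against.** **The dates mostly coincide.** Section 7.1 says so, and each continuation past progression needs sponsor approval. This stands. It limits the number affected, which the documents do not give, but it does not settle the rule for those patients.

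**Clinical progression may mean the end of benefit.** A patient still benefiting under Section 5.10 may not yet have progressed clinically, and Sections 7.1 and 12.1 would then agree. That reading is possible, but Sections 1.1 and 12.2 say only progression, and the term is not defined. It would also do nothing for biopsies taken without progression.

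**A biopsy after a new drug is partly guarded against.** Section 5.2 bars other anticancer agents during participation. Section 5.9 bars most other anticancer treatment until the end-of-treatment visit. Section 6.1 treats the biopsy as part of study participation. A reader might infer from the biopsy mark in the calendar's survival follow-up column that biopsies after later therapy were intended. The documents do not support that: footnote letters in the table and text appear shifted by one, and the mark may denote the post-biopsy visits. What remains is that no sentence requires the biopsy to precede new therapy.

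**The CTC comparison is descriptive.** Draws continue every two cycles after Cycle 5, so a sample near progression is likely to exist. This stands. The need is only to name which sample is paired with the biopsy.

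**Conclusion.** The concern holds as a gap in endpoint definition and analysis set. Sections 7.1, 5.10 and 12.3 together let samples not taken at progression into a test whose hypotheses are defined at progression. For biopsies without progression, the illustrated type I error is 6.0% to 15.1% against 4.8%. That range rests on assumed counts of 1 to 3 and assumed rates of 0% to 25%; the 0% rate is an extreme.

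Three stronger readings are tempting and are not supported.

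- **Late sampling biases the comparison with the historical 50% in a known direction.** Section 2.2.2 gives 24 of 48 tumours after acquired resistance but not when they were sampled relative to RECIST progression or the end of treatment. A mismatch is possible; its size and sign cannot be established.
- **Losing one biopsy badly damages the design.** Power at 17 biopsies is 75.8%, but at 16 it is 79.8%, so the drop from 86.7% is largely discreteness. Section 12.2 already allows for about 6 missing biopsies.
- **The sample-size calculation is wrong.** The 86% reproduces.

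**What to change.** 1. Reconcile Sections 5.10, 7.1, 7.2, 12.1 and the calendar with its footnotes to one defined progression date for the endpoint biopsy and the paired CTC sample. State how it applies when drug continues under Section 5.10.
2. In Section 12.3, limit the primary analysis to biopsies taken at that time point, within a stated window, and before any new systemic anticancer therapy. Report later biopsies, and biopsies without progression, descriptively or as a sensitivity analysis.

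The progression definition and the window are for the sponsor to choose. The documents nowhere name first RECIST progression as the biopsy date, and bringing an invasive procedure forward in a patient still benefiting is a clinical decision. The continuation rule is left as it is.

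**Cost.** The change is to wording only, with no additional biopsy. Some biopsies may need scheduling outside the off-study visit. A few may leave the primary analysis. If fewer than 18 remain, power at a 20% rate is 75.8% with 17, 79.8% with 16 and 64.8% with 15, using cut-offs of 4, 4 and 3 positives. The cut-off should therefore be set by the exact test for the number actually analysed.

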#### 7.1.1 Requirements for Repeat Biopsy

- For Thoracic IR Biopsies: Each patient must be assessed for risk and approved by thoracic interventional radiology as having a candidate lesion that measures at least 8 mm on a chest CT scan and is appropriate for percutaneous biopsy. Risk assessment includes an evaluation of the extent of emphysema and pulmonary fibrosis, risk of procedure-related pneumothorax as estimated by the location of the lesion and the presence of bullous disease in the targeted path of the biopsy needle, and CT evidence of pulmonary arterial hypertension or significant cardiac disease. Lung biopsies will not be performed in patients with chronic lung disease requiring supplemental oxygen at home or in patients with known moderate or severe pulmonary arterial hypertension, valvular disease or cardiomyopathy.
- For Abdominal IR Biopsies: Each patient must be assessed for risk and approved by GI/GU interventional radiology as having a candidate lesion that is appropriate for percutaneous biopsy. Risk assessment includes an evaluation of the risk of bleeding and risk of perforation of visceral structures given the location of the target lesion.
- No aspirin, non-steroidal anti-inflammatory drugs (NSAIDS), or other anti-platelet medication is allowed for 7 days prior to biopsy.
- No low molecular weight heparin is allowed for 12 hours prior to biopsy.
- Prothrombin time must be < 14 seconds, assessed within 2 weeks of biopsy or within 72 hours of biopsy if on chronic warfarin or other anti-coagulation therapy.
- Platelet count must be > 75,000, assessed within 2 weeks of biopsy
- Patients who have a bony metastatic site as the planned site for repeat biopsy, unless there is a significant soft tissue component that can be sampled, as the decalcifying material used to process osseous biopsies denatures DNA and the material is therefore not suitable for molecular analysis.
- Significant co-morbidity or orthopedic condition that may impede optimal positioning during biopsy and/or post-biopsy recovery
- Patients must have an adequate family/caregiver support system to ensure sufficient observation after the outpatient biopsy. If patient does not have a support system, arrangements will be made for overnight admission after the biopsy to observe for potential complications.

CONFIDENTIAL

This document is confidential. Do not disclose or use except as authorized.

### 7.1.2 Procedure for Repeat Biopsy

Once the case is approved by interventional radiology for its appropriateness for biopsy the biopsy will be scheduled and performed in the usual manner. The lesion will be identified by either ultrasound or CT imaging. The interventional radiologist will select a safe path to the lesion. An intravenous cannula will be placed and sedation will be administered as per routine clinical protocol. Typical sedation medications include a combination of intravenous midazolam and fentanyl. Subcutaneous lidocaine will be administered and then a 17-19 gauge metal cannula will be inserted percutaneously into the lesion with visual confirmation by either CT or ultrasound. The interventional radiologist will attempt to obtain two or more 1-2 cm long 18-20-gauge core biopsy samples and three or more 22 gauge fine needle aspirates of tissue using a cutting core biopsy needle or 22 gauge needle. The normal departmental pre-procedural documentation, procedure note documentation and post-procedure observation and discharge algorithms will be performed as per standard practice. Note: biopsies may be obtained at the location of collaborating investigators, i.e. patients are not required to travel to MGH for their biopsies. These centers should follow the procedures as outlined in the protocol or call [name] at MGH to discuss any major variations in biopsy practice from the protocol document.

### 7.1.3 Molecular Assessment of Repeat Biopsy Tissue

Repeat biopsy tumor tissue will be handled under the following procedures. One slide will be routed to anatomic pathology, to confirm that the lesion biopsied is malignant and appears as expected from a histologic standpoint given the presumptive diagnosis. The majority of the sample will undergo genotyping analysis with the SNaPshot platform as described in Section 2.3.1. Note: if the biopsy is taken at another hospital besides Massachusetts General Hospital, anatomic confirmation of the diagnosis should still occur at the hospital performing the biopsy (using as little material as possible). The rest of the material will be formalin-fixed and paraffin-embedded, and should be routed to [name] at MGH for analysis with the SNaPshot platform. Samples should be shipped with a requisition form (see Appendix 4) to:

The primary use of the material obtained from repeat biopsies will be to assess T790M status from resistant specimens. We will also determine if there is MET amplification, another validated mechanism of acquired resistance. However, when there is sufficient tissue, we will perform other exploratory genomic, proteomic and expression profiling and attempt to develop patient-specific tumor models *in vitro* and *in vivo*. The establishment of such models will allow us to functionally validate or refute the hypothesized mechanisms of resistance to BIBW 2992. We have had success with these techniques in the past and will perform these studies in collaboration with [name] who has an established track record of developing xenograft tumor models and cell lines from patient specimens. Leftover material will be returned to the participating institution at the completion of the study.

### 7.1.4 Follow-Up after Repeat Biopsy

All subjects will be seen in clinic for follow-up and assessment of biopsy-related complications at 7 days post-biopsy ( $\pm 2$  days) and again at  $\geq 30$  days post-biopsy.

## 7.2 Circulating Tumor Cell Studies

Blood samples for CTC analysis will be collected at the following time points.

CONFIDENTIAL

This document is confidential. Do not disclose or use except as authorized.

- Day 1, prior to therapy
- Day 1, three hours after dose
- Day 8
- Day 15
- Cycle 2, day 1
- Cycle 3, day 1
- Cycle 4, day 1
- Cycle 5, day 1
- Then every 2 cycles
- At the time of progression (end of study visit)

CTCs will be assessed from each peripheral blood using the CTC-Chip (see Section 2.3.2). This assay will be performed under the supervision of [name]. Blood samples will be same-day couriered to the [name] Lab in the Charlestown Navy Yard at MGH. Blood samples will be stored on a rocking platform to prevent cell settling and will be processed within 24 hours of blood draw. Whole blood will be passed through the CTC-chip using standard procedures as previously published. Captured CTCs will be fixed on the CTC-chip and stained to identify DNA content, epithelial cells and nonspecifically bound leukocytes. Cells staining positive for nuclear content and positive for cytokeratin will be counted as CTCs. The number of CTCs per milliliter of blood will be determined by comprehensive image analysis, scanning the entire chip and identifying CTCs based on cell size, morphology and fluorescence staining. The association of CTC numbers with radiographic disease response and recurrence will be assessed.

Captured CTCs will then be lysed and DNA content will be collected. Allele-specific sensitive methods will be used to determine the T790M status of the captured cells, as previously published. If sufficient material is available, exploratory analyses will also be performed such as whole genome amplification of DNA and analysis with the SNaPshot platform. CTC-based genotypes will then be correlated with tumor-derived genotypes.

